4.3 Study Enrollment Procedures

Recruitment: Clinician referral and advertisement for our program in local newspapers, internet, radio, and television; advertisements through internal research listings distributed via e-mail and posted online by MGH, RSVP for Health (a registry of MGH and Brigham and Women's Hospital where individuals receive information about clinical trials); a listing on ClinicalTrials.gov; flyers posted on hospital-approved bulletin boards or in local health clinics; study-specific postings on Craigslist; meetings with community organizations to recruit non-MGH patients; and study flyers posted at the Bikram Yoga Boston and Bikram Yoga Cambridge studios and on their websites.

Procedures: A Study Coordinator will determine possible subject eligibility by phone, utilizing the IRB approved Depression Clinical and Research Program (DCRP) General Recruitment Protocol (Protocol #: 2007P002312) - once this protocol is added by an approved amendment. Eligible subjects will be invited for a screen visit at the DCRP, where they will complete the consent process with MD or PhD-level staff. Prior to coming in for the screening visit, subjects will be asked to sign up for an online account with both yoga studios," through the Bikram Yoga Boston and the Bikram Yoga Cambridge websites. A screening log will be kept to document reasons for ineligibility and for non-participation of eligible subjects. Consented subjects who continue to meet inclusion criteria will be randomized to hyperthermic yoga or the waitlist control by their baseline visit.

5. STUDY INTERVENTIONS

5.1 Interventions, Administration, and Duration

The study intervention is hyperthermic yoga, and in this case, Bikram Yoga, a form of hyperthermic yoga. The intervention will be community-delivered (free of charge) by two local Bikram Yoga studios, Bikram Yoga Boston and Bikram Yoga Cambridge. Participants will be asked to attend at least two weekly 90-minute classes over the course of an 8-week intervention period at either studio. The intervention period will be followed by a 1-month post-intervention visit; however, during the 1-month period between the active intervention and follow-up visit, yoga will not be provided free to participants. Participants may continue the intervention at their own cost, but this is entirely of their own volition.

Potential Adverse Effects: Bikram Yoga is performed in a heated room (105-110°F), which may be uncomfortable. Discomfort may include cramping or feeling hot, lightheaded, dizzy, fatigued, or nauseous. More extreme and less frequent heat related risks include fainting, heat stroke, or cardiovascular events. Hydration is the best way to avoid these reactions to the heat, as such hydration recommendations will be provided to participants during their baseline visit prior to their first yoga class (i.e., an additional four 8 oz servings of water pre- and post-yoga classes). Bikram Yoga instructors may encourage participants to stay in the heated room

despite feeling overwhelmed, though they are free to leave the room – this point is emphasized during their baseline visit. Participation in yoga classes could also potentially aggravate old injuries and/or cause new injuries. Women experiencing hot flashes related to perimenopause or menopause may experience increased discomfort in the heated yoga room; however, there is no reason to believe that participation is unsafe. Stimulant and recreational drug use during the study may increase subject risk for heat related side effects during yoga classes (e.g., fatigue, nausea, dizziness). It is possible that participants may experience feelings of frustration and/or self-criticism due to the intensity of the exercise.

5.2 Handling of Study Interventions

The infrastructure of the MGH DCRP will permit blinded MD and PhD-level clinician assessors or psychology interns (under supervision by a licensed clinical psychologist) at no additional cost to the study. Any unblinded assessors (MD and PhD- level staff or psychology interns designated prior to the start of the study) will not have access to data nor involvement in data monitoring or analyses. All psychology interns are closely supervised by MD and PhD-level staff, and are trained in the administration and rating of depression diagnostic scales.

Blinded DCRP assessors will perform primary and secondary endpoint collection. The research assistant welcoming the subject will remind the subject not to unblind the blinded assessors at each assessment visit. The research assistant will not be blinded, as they will be collecting attendance data from the yoga studios. If assessment visits are conducted by phone (on an as needed basis to reduce subject burden), blinded assessors will remind participants not to unblind them at the beginning of the call.

5.3 Concomitant Interventions

5.3.1 Allowed Interventions

Psychotropic medication use, other than stimulants, and ongoing stable psychotherapy (individual or group) is allowable as long as medications/psychotherapy have been stable for at least two months and at a stable dose for at least 4 weeks prior to screening visit.

If during the study subjects require regular care (i.e., worsening depression or safety issues) and do not have a provider, they will be allowed to begin 3-month free follow-up psychiatric care at DCRP and will be discontinued from the intervention at study clinician's discretion.

5.3.2 Required Interventions

N/A

5.3.3 Prohibited Interventions

Use of stimulant medications or diet pills, or any pre-workout powders or liquids designed to provide excessive energy are exclusionary. The consumption of coffee or other caffeinated beverages is acceptable.

5.4 Adherence Assessment

Participants are asked to attend at least two weekly hyperthermic yoga classes over an 8-week intervention, a minimum total of 16 yoga classes. Adherence will be defined at 75% of the minimum prescribed dose of the study intervention – i.e., adherence means that participants attended at least 12 out of 16 yoga classes over the 8-week study intervention period. The two yoga studios track attendance via computer systems. Attendance data will be collected by study staff (usually a research assistant) who will either email via Send Secure email, or utilize Dropbox to communicate with the studio owners, [name] (Bikram Yoga Boston) and [name] (Bikram Yoga Cambridge), to obtain attendance data. All yoga students, whether study participants or not, are required to sign in at the front desk of the studios prior to class.

Yoga instructors act as front desk attendants for their own classes and sign participants into the computer system at this time.

Fidelity Assessment: The adherence of each of the two Bikram Yoga studios to the Bikram Yoga protocol will be established, prior to starting the proposed study and every six months thereafter with an adherence measure designed by [name].

Temperature Measurement: We will measure the temperature and humidity in the three heated yoga rooms with HOBO Bluethooth Low Energy Temperature/Relative Humidity Data. HOBO MX1101 data logger measures and transmits temperature and relative humidity data wirelessly to mobile devices via Bluetooth Low Energy (BLE) technology. These devices will be mounted in each of the three rooms. Study staff will collect data prior to study initiation and quarterly thereafter to monitor temperature and humidity- and to store the data for later analyses. These devices provide wireless and time stamped temperature and humidity data to smart phone device. The self-contained wireless data logger works with Onset's free HOBOmobile app for logger setup and data management. Data is accessible anytime from a mobile device for iOS or Android over a 100-foot range.

6. STUDY PROCEDURES

6.1.1 Immediate Yoga Group (IYG) Schedule of Evaluations

Assessment	V1	V2	V3	V4	V5	V6***	V7	V8	V9	V10	V11	V12
Informed Consent Form	X											
Demographics/Contact Information	X											
Clinician-Administered Psychiatric History Form	X											
Inclusion/Exclusion Criteria	X											
Safety Labs (collected by research coordinator)	X											
1. Blood												
2. ECG												
3. Urine drug screen												
4. Urine pregnancy test (Female)												
Medical History	X											
Physical Examination by DCRP psychiatrist	X					X	X					
Habits Questionnaire	X					X	X					
MINI	X											
C-SSRS (lifetime and past year V1; since last visit all other visits)	X				X	X	X					
Reproductive Status Questionnaire (Female)	X											
IDS-CR	X	X	X	X	X	X	X					
HAM-D-28		X				X	X					
Self-Rated Questionnaires: STAI; SF-36; Q-LES-Q; EIFI; PSS; PSQI; FFMQ; RRS, URICA	X	X	X	X	X	X	X					
URICA		X				X						
Concomitant Medications	X	X	X	X	X	X	X					
Vital Signs collected by research coordinator	X	X	X ⁺	X ⁺	X	X	X					
Randomization		After baseline visit										

Psychoeducational Session		X											
Waist-to-Hip Ratio measured by research coordinator		X			X	X	X						
Physiological Markers 1. Inflammatory markers (blood) 2. Cortisol (salivary)*		X			X	X	X						
Sleep Diary		X			X	X	X						
Adverse Events		X	X	X	X	X	X						
Hot Yoga Beliefs Scale		X				X	X						
Acceptability Interview						X							
MINI Mood Module						X	X						
QIDS-C and Weekly Phone Monitoring Form		-----> On weeks in between V2-V3, V3-V4, V4-V5, V5-V6 and V6-V7											
Pre- and Post-Yoga Scales (STAI State, EIFI)		30 minutes prior to and 30 minutes post each yoga class											

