6.2.1 Screening Evaluation

Consenting Procedure

Prior to engaging in any study related activities, informed consent will be obtained by an MD- or PhD-level clinician or supervised psychology intern at the DCRP. One informed consent will be obtained for the screening and study procedures. Patients will be informed during the consent process that their participation is voluntary and their relationship with their prescribing physician will be unaffected by any choice to discontinue study participation. All participants will be informed that they can decline to answer any questions that they find upsetting and may withdraw from study participation at any time. The consent form will include the study procedures, information about potential risks and benefits of participation, and information regarding who they can contact with further questions or concerns. Patients will be alerted to the nature of the hyperthermic yoga practice during the consent process. Participants will have 24-hour pager access to an internal medicine physician, [name], whose specialty is in alternative medicine. This information will be given in the consent form. Documentation of informed consent will be kept in the Documentation of the Informed Consent Process for Onsite Subject File.

Visit 1: Screen – IYG and DYG

The screening visit will last approximately 3 hours. The purpose of this visit is to determine study eligibility. The two Figures above (6.1.1 and 6.1.2) outline the procedures for the screening visit, which are the same for the IYG and DYG. All of the screening items will be completed prior to the baseline visit (within 21 days of the screening visit).

- Informed Consent Form
- Demographics/Contact Information
- Clinician-Administered Psychiatric History Form
- Inclusion/Exclusion Criteria
- Safety Labs (i.e., blood, ECG, urine drug screen, urine pregnancy test [female] collected by a trained research coordinator)
 - Blood draw: A phlebotomy trained research coordinator at the DCRP will draw 11mL of blood (one 8mL tiger top tube and one 3mL lavender top tube).
- Medical History
- Physical Examination conducted by DCRP psychiatrist
- Habits Questionnaire
- MINI
- C-SSRS Lifetime and Past Year
- Reproductive Status Questionnaire (female)
- IDS-CR
- Self-Rated Questionnaires: STAI, SF-36, Q-LES-Q, EIFI, PSS, PSQI, FFMQ, RRS
- Concomitant Medications

- Vital signs
- Give salivettes and instructions to bring back salivary cortisol samples to their baseline visit

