6.2.4 Follow-up Visits

Phone visits will occur bi-weekly from baseline through the end of the study intervention period. During the 1 month follow-up period, there will be a phone call during the midpoint (2-weeks into the follow-up period).

Assessment visits will be completed within a reasonable time frame (+/- 3 workday window), but may occur outside this window if deemed appropriate by study staff.

Visit 3 (Week-1 Assessment)* – IYG and DYG

- IDS-CR
- Self-Rated Questionnaires: STAI, SF-36, Q-LES-Q, EIFI, PSS, PSQI, FFMQ, RRS
- Concomitant Medications
- Vital Signs⁺
- Adverse events

Visit 4 (Week-3 Assessment)* – IYG and DYG

- IDS-CR
- Self-Rated Questionnaires: STAI, SF-36, Q-LES-Q, EIFI, PSS, PSQI, FFMQ, RRS
- Concomitant Medications
- Vital Signs⁺
- Give salivettes
- Give Sleep Diary (can bring to the following visit as long as it was completed for the right week)
- Adverse Events

Visit 5 (Week-5 Assessment) – IYG and DYG

- C-SSRS since Last Visit
- IDS-CR
- Self-Rated Questionnaires: STAI, SF-36, Q-LES-Q, EIFI, PSS, PSQI, FFMQ, RRS
- Concomitant Medications
- Vital Signs
- Waist-to-Hip Ratio
- Physiological Markers (i.e., inflammatory markers [blood], cortisol [saliva])
- Give salivettes
- Collect and give Sleep Diary (can bring to the following visit as long as it was completed for the right week)
- Adverse Events

Visit 8 (Week-1 Yoga Assessment) – DYG

- IDS-CR
- Self-Rated Questionnaires: STAI, SF-36, Q-LES-Q, EIFI, PSS, PSQI, FFMQ, RRS
- Concomitant Medications
- Vital Signs⁺
- Adverse Events

Visit 9 (Week-3 Yoga Assessment) – DYG

- IDS-CR
- Self-Rated Questionnaires: STAI, SF-36, Q-LES-Q, EIFI, PSS, PSQI, FFMQ, RRS
- Concomitant Medications
- Vital Signs⁺
- Give salivettes
- Give Sleep Diary
- Adverse Events

Visit 10 (Week-5 Yoga Assessment) – DYG

- C-SSRS since Last Visit
- IDS-CR
- Self-Rated Questionnaires: STAI, SF-36, Q-LES-Q, EIFI, PSS, PSQI, FFMQ, RRS
- Concomitant Medications
- Vital Signs
- Waist-to-Hip Ratio
- Physiological Markers (i.e., inflammatory markers [blood], cortisol [saliva])
- Give salivettes
- Collect and give Sleep Diary (can bring to the following visit as long as it was completed for the right week)
- Adverse Events

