8. INTERVENTION DISCONTINUATION

If a subject's overall depressive symptoms significantly increase, or if a subject develops suicidal intent, he/she will be evaluated by a study clinician to determine if referral for clinical intervention is needed. This will be determined per study clinician judgment.

- Subjects who demonstrate an increase in the IDS total score of 25% or greater over baseline or whose QIDS-C score is a >16 (indicating severe depression) will be assessed for referral to evidence-based clinical treatment.
- A “yes” on items 4 or 5 on the Columbia-Suicide Severity Rating Scale, a score of 3 on the suicidal ideation question of the QIDS-C, or a score of 3 on the IDS-CR suicide item will prompt assessment, and if necessary, appropriate referral.
- If a subject reports that worsening severity is due to situational factors and there appears to be no acute risk of self harm or other significant worsening, they will be given the option to be reassessed within 72 hours (most likely via phone) to determine the safety of continuation.
- Patients will also be dropped from the study if they are, in the judgment of the study clinician, deemed to be a safety risk, the intervention appears to making their condition worse, or if new information is uncovered re: an untreated condition (e.g., onset of substance abuse or physical condition) that would affect participation or threaten the integrity of the study.

Disconsolation due to Non-Adherence: if a subject does not attend a yoga session for two weeks, he or she will be discontinued from the intervention – though he or she will be asked to come in for a final assessment visit. If a subject misses more than two consecutive assessment visits, he or she will also be discontinued from the intervention, unless there are extenuating circumstances communicated to the study team. Subjects will be allowed to continue if they are only attending one yoga class during any specified week, though this will be controlled for in analyses – their data will still be useful. If subjects are discontinued from the intervention, they will be included in the modified ITT (MITT) analyses (see section 9 below) and invited for a Visit 6 (final exit visit).

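### As written, the follow-up C-SSRS looks back only to the previous visit, so on the planned schedule its recall misses screening to week 3 and, in the DYG, V6 to yoga week 3

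*Combined protocol and SAP*

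**What the plan says.** The recall label is the same in both schedules of evaluations (6.1.1 and 6.1.2): "C-SSRS (lifetime and past year V1; since last visit all other visits". The scale is marked at these visits:

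- immediate yoga group (IYG): V1, V5, V6 and V7;
- DYG: V1, V5, V6, V10, V11 and V12.

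The visit lists in 6.2.1 to 6.2.5 agree with the tables. Screening has "C-SSRS Lifetime and Past Year". V2, V3 and V4, and in the DYG V7, V8 and V9, have no C-SSRS. V5 and V10 list "C-SSRS since Last Visit", and 6.2.5 uses the same recall for V6, V11 and the one-month visits.

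The visits without a C-SSRS are still numbered study visits. The one before V5 is "Visit 4 (Week-3 Assessment)* – IYG and DYG" and the one before V10 is "Visit 9 (Week-3 Yoga Assessment) – DYG". On timing before baseline, 6.2.1 says: "All of the screening items will be completed prior to the baseline visit (within 21 days of the screening visit".

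Section 8 uses a positive answer on "items 4 or 5 on the Columbia-Suicide Severity Rating Scale" as one of three alternative prompts for assessment. The other two are a score of 3 on the QIDS-C suicidal ideation question and a score of 3 on the IDS-CR suicide item.

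**The concern.** A recall period that runs back to the previous visit gives continuous cover only if the scale is given at every visit. Here it is given at some visits, and the recall label was not adjusted. A rater who follows the label at V5 asks about the time since V4, and at V10 about the time since V9. Time before those visits, back to the preceding C-SSRS, is asked about on no form.

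In both groups the uncovered time includes the interval between the screening C-SSRS and randomization. It also includes the first three weeks of yoga: weeks 0 to 3 in the IYG, and yoga weeks 0 to 3 in the DYG. An episode of ideation with intent that arose and subsided in that time would not appear on the C-SSRS, although items 4 and 5 are a named prompt in section 8. Because the anchor is undefined, raters could also use different windows, and their C-SSRS records would then not be comparable.

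**Working it through.** The protocol gives no figure of its own to reproduce, so the check is a map of recall windows against visits.

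**Inputs.**
- V2 = week 0, V3 = week 1, V4 = week 3, V5 = week 5, V6 = week 8 (6.2.2, 6.2.4, 6.2.5).
- DYG yoga clock starting at V7: V8 = yoga week 1, V9 = yoga week 3, V10 = yoga week 5 (6.2.4).
- V1 to V2: 0 to 21 days, taking the 21 days in 6.2.1 as the upper limit.
- DYG V6 to V7: not fixed in the protocol; 0 to 2 weeks is assumed. Section 3 gives total durations of about 24 and 15 weeks. The difference is 9 weeks; less the 8-week wait, this leaves about 1 week.
- The visit windows of 3 workdays either way (6.2.4) are ignored.

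**Windows under the two possible anchors.**

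| C-SSRS at | Since the previous visit | Since the previous C-SSRS |
|---|---|---|
| V5, both groups | week 3 to 5 | screening to week 5 |
| V6, both groups | week 5 to 8 | week 5 to 8 |
| V7, IYG | week 8 to follow-up | week 8 to follow-up |
| V10, DYG | yoga week 3 to 5 | V6 to yoga week 5 |
| V11, DYG | V10 to V11 | V10 to V11 |
| V12, DYG | V11 to V12 | V11 to V12 |

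Only V5 and V10 differ, because only they follow a visit without the scale.

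**Gap 1, both groups, V1 to V5.** Uncovered share = (s + 35 − 14) / (s + 35), where s is the screening interval in days.
- s = 0: 21/35 = 60%, or 3 weeks.
- s = 21: 42/56 = 75%, or 6 weeks.

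In the IYG this includes the first 3 of the 8 yoga weeks (3/8 = 37.5%).

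**Gap 2, DYG only, V6 to V10.** Uncovered share = (g + 5 − 2) / (g + 5), where g is the V6 to V7 interval in weeks.
- g = 0: 3/5 = 60%.
- g = 1: 4/6 = 67%.
- g = 2: 5/7 = 71%.

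**With the anchor at the last C-SSRS,** the uncovered time is 0 weeks in both groups.

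**Other cover in the same periods.** The IDS-CR is given at every visit and looks back seven days (9.5.1). The QIDS-C and phone monitoring form are scheduled between visits from V2 onward (6.1.1, 6.1.2), and the bi-weekly calls ask about suicidality (section 7 and 7.3). Before baseline there are no calls. The baseline IDS-CR reaches back 7 days, so up to 21 − 7 = 14 days between screening and baseline have no scheduled suicide-specific instrument looking back on them. Adverse events are, however, recorded at V2.

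**The case against.** The strongest reply is that the gap depends on one reading of an undefined phrase. The wording may simply name the version of the form, and a sensible rater at V5 would ask about the time since the C-SSRS was last given. The form itself is not in the documents, so actual use cannot be checked. This stands. What the documents show is a written rule that produces a gap if followed literally, not proof that data were or will be lost. Even on the literal reading, a participant who misses V4, or who has the early discontinuation visit before week 3, would have part of the time covered.

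A reader might infer that suicidality goes unmonitored in the first weeks of yoga. The documents do not support that. In those weeks there are IDS-CR assessments at weeks 1 and 3, the QIDS-C and phone calls between visits, and adverse event recording at visits. Nor is the C-SSRS the only prompt in section 8; either of the other two items is enough by its own wording. They do not, however, supply C-SSRS items 4 and 5 for the missing period.

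A reader might also infer that a reported C-SSRS result would be too low, or that the arms would be compared unfairly. The C-SSRS is not among the outcomes in 9.5, and 9.6 plans no analysis of it. Before crossover the C-SSRS schedule is identical in the two groups, so no between-arm bias follows.

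Finally, a longer recall at V5 would find a past episode late and would not detect it sooner. That also stands: the gain is a complete and consistent record, while timely detection rests on the other instruments.

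**Conclusion.** The point holds as a conflict between the recall wording and the visit schedule. Followed literally on the planned schedule, the C-SSRS leaves 3 to 6 weeks between screening and week 3 unasked in both groups. In the DYG it leaves a further 3 to 5 weeks between V6 and yoga week 3. The first range rests on a screening interval of 0 to 21 days, the second on an assumed V6 to V7 interval of 0 to 2 weeks. The upper ends are worst cases. If raters already anchor to the last C-SSRS, both gaps are zero.

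The consequence is limited to the C-SSRS record. Cover by other means is thinnest between screening and baseline, before the calls begin. The correction is worth making because the written rule itself creates the gap in a named safety prompt, and closing it takes little.

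**What to change.** In 6.1.1, 6.1.2, 6.2.4 and 6.2.5, reconcile the recall wording with the schedule: replace the since-last-visit label with *since the last C-SSRS was completed*, and print the date of that C-SSRS on the form. V5 then covers screening to week 5, V10 covers V6 to yoga week 5, and a missed C-SSRS no longer opens a new gap.

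No visit, instrument or clinical rule is added. The cost is one wording change, one date field, and a longer recall at two visits: 5 to 8 weeks at V5 (35 to 56 days) and 5 to 7 weeks at V10 under the same assumptions, in place of 2 weeks at each.
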